6.0 Summary of Proposed Placebo Controlled Trial

Our objective is to determine (through the performance of an adequate and well-controlled clinical trial) if the administration of Fisetin (FIS) safely reduces inflammation and pain, reduces senescent cell burden, mitigates cartilage degeneration, and improves joint function in patients with moderate to severe OA of the knee.

Patients suffering from OA of one or both knees will be recruited from the clinical practice of the Principal Investigator at TSC. Patients diagnosed with Kellgren-Lawrence grade II-IV OA of the knee via radiographic analysis, who meet all enrollment criteria will be offered the opportunity to participate in this study.

At the first visit, each potential subject will be fully informed regarding all aspects of the proposed study and will be required to review and sign a full, IRB approved, Informed Consent Form (ICF) attached as **Appendix A in Section 22.1**. Subjects who sign Informed Consent will be screened by a member of the Study Team. The patients' medical record will be reviewed to determine if medical history indicates that the eligibility criteria are met. If so, subjects will be screened for OA and senescent cells by T-Cell assay, C12FDG Flow assay, and by senescence biomarker assay. Further blood analyses will be performed.

Subjects who meet eligibility criteria will be assigned, 1:1 via block randomization, to one of the two blinded study groups. FIS and the inactive placebo are collectively referred to as Study Medication.

n=36: Active Treatment: FIS: 100 mg capsules (~20 mg/ kg/ day);

n=36: Placebo Control: Appearance matched capsules (dose to match the number of capsules as if subjects were receiving active treatment).

At visit two, Quantitative MRI, kinematic movement and strength testing, range of motion (ROM) and functional performance testing. Subjects will complete numerous patient reported outcomes tools, including an augmented patient reported outcomes (PROs), including numerical rating scale (NRS) for pain (as described in **Section 11.5**) of this protocol International Knee Documentation Committee (IKDC), Lysholm, Tegner, Western Ontario McMaster Universities Osteoarthritis Index (WOMAC) and short form-12 health survey (SF-12), which will provide a baseline assessment of joint pain and function.

After randomization is performed, a Study Team member will then inform the Vail Hospital pharmacist of the subject's assigned randomization code, and the medication will be obtained from the pharmacy. Subjects will take their first dose of study medication at the clinic.

Then, subjects will self-medicate on day 2 followed by 28 days off. A second course will be taken for two consecutive days (days 31 and 32). Day 1 will be defined as the first day of intake of the Study Medication. A Medication Log recording medication administration will be maintained by the subject during the period of administration.

Subjects will complete an augmented NRS pain scale. This will be completed electronically once every 3 days for 6 weeks after the first dose and then weekly thereafter for an additional 6 weeks.

Subjects will return to the clinic for a blood draw (visit 3) 2 weeks after the first dose of study medication (+/- 2 days).

Subjects will be called on the telephone three times during study medication administration to capture adverse events and to remind subjects to take the next dose of study medication.

On the fourth visit (2 weeks after the last medication dosage +/- 10 days) subjects will be asked to return to the study site. A review of study medication and concomitant medication use, vital signs, and a physical exam with ROM will be performed. The subject will be asked to complete the augmented NRS, IKDC, Lysholm, TEGNER, WOMAC and SF-12. All adverse events and protocol deviations will be documented. A blood draw will be performed to measure senescent cells by T-Cell assay and by senescence biomarker assay. Further blood analyses will be performed.

At 6-, 12- and 18-months post first dose of Study Medication, subjects will be asked to complete the augmented NRS, IKDC, Lysholm, TEGNER, WOMAC and SF-12 remotely, either electronically or on paper.

At 6- and 12-months post first dose (Visits 5 and 6) subjects will be evaluated at the study site. A review of concomitant medications, vital signs, and a physical exam with ROM will be performed. All adverse events and protocol deviations will be documented. A blood draw will be performed to measure senescent cells by T-Cell assay and by senescence biomarker assay. Further blood analyses will be performed. A quantitative MRI, lower-extremity kinematics testing with video motion analysis, isokinetic dynamometry testing, and functional performance testing will be performed.

adverse event and protocol deviation data will be collected.

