	
 3. Vital signs; 4. Medical and surgical history; 5. Demographic information; 6. Details of injury; 7. Severity of injury; 8. Medications; 9. Physical exam with range of motion (ROM) of the target limb; 10. BMI; 11. Urine pregnancy test for Women of Child Bearing Potential (WOCBP); 12. Blood analysis; 13. Completion of augmented PROs, including: NRS, IKDC, Lysholm, TEGNER, WOMAC and SF-12; 14. A radiograph of the target knee will be performed to confirm the presence of Kellgren-Lawrence grade II-IV OA; 15. The patients' medical record will be reviewed, and the subject will be interviewed to determine if inclusion/exclusion criteria are met; 16. Randomization. 
Patients who have met all eligibility criteria will be assigned, 1:1 via block randomization, to one of the two blinded study groups.
 
Visit 2 (Baseline) (Within 3 months of Visit 1)
 
Some procedures performed in this visit may be performed in Visit 1 provided that Informed Consent has been signed.
 
 1. Urine pregnancy test for Women of Child Bearing Potential (WOCBP) 2. Quantitative MRI; 3. Kinematic movement; 4. Assessment of muscle strength, isokinetic dynamometry; 5. Functional performance testing.
--	---

	
After randomization is performed, a Study Team member will then inform the Vail Hospital pharmacist of the subject's assigned randomization code the study medication will be obtained. The subject will take the first dose of study medication at the clinic.
 
Subjects will be instructed to self-medicate for day 2 followed by 28 days off. They will be instructed to begin a second course of treatment for two consecutive days (days 31 and 32).
 
Subjects will be reminded at Visit 3 in-person and over the phone 2-4 days prior to the last dosing of study medication about their upcoming dosing. If applicable, they will also be reminded to withhold current medications as instructed by the PI.
 
A Medication Log recording medication administration will be provided to the subject with instructions to complete during the period of administration.

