10.1 Visit 2 (Baseline): (Within 3 months of Visit 1)

Some procedures performed in this visit may be performed in Visit 1 provided that Informed Consent has been signed.

1. Urine pregnancy test for Women of Child Bearing Potential (WOCBP)

-
2. Quantitative MRI;
 3. Kinematic movement;
 4. Assessment of muscle strength, isokinetic dynamometry;
 5. Functional performance testing.

After randomization is performed, a Study Team member will then inform the Vail Hospital pharmacist of the subject's assigned randomization code, and obtain study medication. Subjects will take their first dose of study medication at the clinic.

Subjects will be instructed to self-medicate for day 2 followed by 28 days off. A second course will be taken for two consecutive days (days 31 and 32).

A Medication Log recording medication administration will be provided to the subject with instructions to complete during the period of administration.

10.2 Visit 3: Two Weeks after first dose of Fisetin or Placebo (+/- 2 days)

All subjects will return to the study site 2-weeks from the subject's last dose of Fisetin or placebo. The following procedures will be performed:

1. Blood Analysis.

10.3 Visit 4: Two Weeks from the Subject's Last Dose of Fisetin or Placebo (+/- 10 days)

All subjects will return to the study site two-weeks from the subject's last dose of Fisetin (FIS) or placebo. The following procedures will be performed:

1. Vital signs;
2. Medical and surgical history;
3. Physical exam with ROM of target limb;
4. Blood analysis;
5. Medications;

-
6. Completion of augmented PROs, including: NRS, IKDC, Lysholm, TEGNER, WOMAC and SF-12;
 7. Protocol deviation assessment;
 8. Adverse event assessment.

10.4 Visit 5: Six Months from the Subject's First Dose of Fisetin or Placebo (+/- 4 weeks)

1. Vital signs;
2. Medical and surgical history;
3. Physical exam with ROM of target limb(s);
4. Blood analysis;
5. Completion of augmented PROs, including: NRS, IKDC, Lysholm, TEGNER, WOMAC and SF-12;
6. Medications;
7. Protocol deviation assessment;
8. Adverse event assessment;
9. Quantitative MRI;
10. Lower-extremity kinematic testing with video-motion analysis;
11. Isokinetic dynamometry testing;
12. Functional performance testing.

10.5 Visit 6: 12 Months following First Dose of Study Medication (+/- 4 weeks)

All procedures performed in Visit 5 will be repeated.

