10.8 Phone Calls

Subjects will be contacted by phone three times while they are taking study medication to remind them to take the next dose of drug and to capture any adverse events.

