22.2 Appendix B – Study Schemata

Visit Type	Screening	Baseline (4)	Emailed patient questionnaires	Safety Blood Draw	Phone Calls	Study Visit	Study Visit	Study Visit	Emailed patient questionnaires	Unscheduled
Clinic Visit Number	1	2		3		4	5	6		
Visit Date			Every 3 days for 6 wks after first dose of study drug and weekly for 6 wks thereafter	2 weeks after first dose of study drug	3 times after first dose of study drug	2 weeks after last dose of study drug	6 months after first dose of study drug	12 months from first dose of study drug	18 months after first dose of study drug	As needed for AEs/SAEs
Acceptable Visit Window		within 3 months of screening	± 1 day	± 2 days		± 10 days	± 4 weeks	± 4 weeks	± 4 weeks	N/A
Procedures & Assessments										
Informed Consent (1)	X									
Randomization (Placebo or Fisetin) (5)	X	X								
Medical/Surgical History & Demographics	X									
Physical Exam with Range of Motion of Study Knee	X					X	X	X		X
Vitals	X	X				X	X	X		X
BMI	X									
Record concomitant medications & supplements	X	X				X	X	X		X
Blood Draw (6)	X	X		X		X	X	X		X
Urine pregnancy test for WOCBP (2)	X	X								
PRO questionnaires			X			X	X	X	X	
Radiograph of Study Knee (3)	X									
Quantitative MRI		X					X	X		
Biomotion tests (functional performance, joint range of motion, muscle strength, video motion analysis)	X	X					X	X		
Dispense study drug		X								
Provide study drug diary		X								
Return study drug and diary						X				
Review and Assess AEs and SAEs				X	X	X	X	X		X

FOOTNOTES:

(1) Informed consent must be signed by the patient prior to ANY research-related procedures. The informed consent document can only be signed by the study PI and/or the treating clinician (MD/NP/PA) who is on the protocol.
(2) WOCBP = Women of Child Bearing Potential
(3) To confirm the presence of Kellgren-Lawrence grade II-IV OA.
(4) Procedures at Baseline may be performed at the Screening Visit after the Informed Consent Form (ICF) is signed.
(5) Randomization can occur at Screening or Baseline as long as the ICF has been signed and patient eligibility in the study is confirmed.
(6) If the Baseline visit occurs greater than 3 months after the Screening Visit, blood should be collected again for safety purposes.

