22.3 Appendix C-Augmented Numerical Rating Scale

THE STEADMAN CLINIC
AND
STEADMAN PHILIPPON RESEARCH INSTITUTE

APPROVED

Clinical Trial #2019-16: Pain Questionnaire

Greetings from The Steadman Clinic!

This short pain questionnaire is part of the clinical trial that you are participating in at The Steadman Clinic.

We thank you very much for your time!

If you have missed an item, it will appear in **RED**. At the end of the , there is a submit button. Once you click the submit button, a new page with a "Thank You for Your Response" message will appear.

There is no need to print this form.

On a scale of 0 to 10 please describe your current level of knee pain:

Today: 0 - No Pain 1 2 3 4 5 6 7 8 9 10 - Severe Pain

At its worst: 0 - No Pain 1 2 3 4 5 6 7 8 9 10 - Severe Pain

Following activity: 0 - No Pain 1 2 3 4 5 6 7 8 9 10 - Severe Pain

Please select the one response that best reflects your knee pain:

- None or you ignore it Moderate pain, tolerable but concessions to pain are made.
 Slight, occasional, no compromise in activity Marked pain, serious limitations of activity
 Mild, no effect on average activities Totally disabled, crippled, pain in bed, bedridden

After 6 to 9 blocks (about 1 mile), please describe how you would walk: *

- No limp Slight limp Moderate limp Severe limp

How much trouble do you have with...

Stiffness in your knee? * NONE MILD MODERATE SEVERE EXTREME

Decreased motion of your knee? * NONE MILD MODERATE SEVERE EXTREME

How would you rate your current level of function? *

- Normal Nearly Normal Abnormal Severely Abnormal

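### No scheduled adverse-event question is guaranteed between the last home dose on day 32 and Visit 4, which falls 4 to 24 days later

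*Combined protocol and SAP*

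**What the plan says.** Adverse events are the primary endpoint (Sections 8.2.1 and 15.5.1). Study medication is taken on days 1, 2, 31 and 32. The day 1 dose is taken in clinic and day 2 is self-medicated; no visit is scheduled on days 31 or 32.

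The three telephone calls are described in several places:

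- Section 6.0: subjects are "called on the telephone three times during study medication administration to capture adverse events and to remind subjects to take the next dose".
- Section 10.8, with near-identical wording in the synopsis: subjects are "contacted by phone three times while they are taking study medication to remind them to take the next dose of drug", and the calls also capture adverse events.
- Synopsis, under Visit 2: subjects are reminded "over the phone 2-4 days prior to the last dosing of study medication about their upcoming dosing". This is the only call with a stated date.
- Appendix B: the calls occur "3 times after first dose of study drug". The window cell is blank, and adverse-event review is marked for the calls.

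The next scheduled contact with adverse-event review is the one headed "10.3 Visit 4: Two Weeks from the Subject's Last Dose of Fisetin or Placebo (+/- 10 days". In between, subjects complete the form in Appendix C every 3 days for 6 weeks after the first dose and then weekly. It opens with "On a scale of 0 to 10 please describe your current level of knee pain" and continues with pain category, limp, stiffness, motion and knee function. No item asks about other symptoms.

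**The concern.** Section 13.1 lists reduced appetite, altered activity, nausea, dry mouth, diarrhea, vomiting and fatigue as potential side effects of fisetin. Symptoms of this kind can be short-lived and mild, so whether they reach the case report form depends largely on when the subject is asked. Section 12.2.3 itself says that events attributed to the study medication generally arise close in time to dosing.

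The second course is where this trial adds most to what is known. Section 5.4 reports 36 subjects treated under the referenced IND, of whom only 4 were dosed in two consecutive months. The second course is also taken wholly at home, and the visit after it has a wider window (±10 days) than the visit after the first course (±2 days).

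If brief symptoms are missed in both arms, observed rates fall and the absolute difference between arms shrinks. Section 15.1 hypothesizes that fisetin will not show a higher adverse-event rate, so this error leans toward the hoped-for conclusion.

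**Working it through.** The check is date arithmetic followed by a comparison of the sections.

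**Inputs.** Dosing days 1, 2, 31 and 32 (Sections 6.0 and 7.4.1). Visit 4 at 14 ± 10 days after the last dose (Section 10.3). Dated reminder 2 to 4 days before the last dosing (synopsis). Form every 3 days for 6 weeks (Section 10.6.1).

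**Visit 4.**
- Earliest: 14 − 10 = 4 days after the last dose, day 32 + 4 = 36.
- Nominal: day 32 + 14 = 46.
- Latest: 14 + 10 = 24 days after the last dose, day 32 + 24 = 56.
- Measured from the day 31 dose, the range is 36 − 31 = 5 to 56 − 31 = 25 days.

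**The dated call.** If the last dosing means day 32, the call falls on days 32 − 4 = 28 to 32 − 2 = 30. If it means the course starting on day 31, it falls on days 27 to 29. Either way it comes before the second course.

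**The other calls.** Four dosing days less the clinic dose leaves three home doses (days 2, 31, 32), which matches the number of calls. If each call reminds the subject of one home dose, the third comes before the day 32 dose. It might fall after the day 31 dose and so ask about that one, but it cannot cover the completed course.

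**The form.** Counting every 3 days from day 1 (an assumed start), forms fall on days 34, 37, 40 and 43. That is four contacts in the first 11 days after the last dose (43 − 32 = 11), none of which asks about anything except the knee.

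**Sections side by side.** Sections 6.0 and 10.8 and the synopsis confine the calls to the dosing period and pair adverse-event capture with a next-dose reminder; after day 32 there is no next dose. Appendix B sets only a lower limit, the first dose. Staff following Section 10.8 would finish calling by day 32, while staff following Appendix B could call later. No section requires a call after day 32.

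**The case against.** A reader might infer that no call can follow the last dose. The documents do not support that. Appendix B leaves the upper limit open, adverse-event capture is a stated purpose separate from the reminder, and no section says every call must precede a dose. Nor can one say that second-course side effects are first asked about at Visit 4, since a call between the day 31 and day 32 doses could ask about day 31.

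Other routes also exist. Section 12.2 encourages spontaneous reports and requires all events since the previous visit to be recorded at each visit or whenever reported. Section 12.2.6 tells subjects to contact the site immediately for a systemic reaction. Section 10.7 covers unscheduled contacts. These points stand, and they limit the gap to scheduled, solicited questioning. They help least with mild gastrointestinal symptoms or fatigue, which are the least likely to prompt a call from the subject.

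A reader might also attach a large power loss. Assume 36 per arm, true symptom rates of 40% versus 10% per course, and a two-sided 5% Fisher test. A comparison restricted to the second course falls from 80% power at full capture to 35% at half capture. The plan makes no such comparison; Section 15.5.1 compares groups, not courses. On the same assumed rates, take any symptom over both courses, with courses independent and the first fully captured. The per-subject rates are then 1 − 0.6 × 0.6 = 64% versus 1 − 0.9 × 0.9 = 19% at full capture, and 1 − 0.6 × 0.8 = 52% versus 1 − 0.9 × 0.95 = 14.5% at half capture. Power falls only from about 97% to about 91%, and not at all if the same subjects react both times. Event-count analyses could lose more. None of these rates or capture shares comes from the documents, so neither calculation measures the harm.

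Finally, no between-course contrast is planned, so a claim that the second course will look better tolerated than the first goes beyond the plan.

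**Conclusion.** The point holds in a limited form. Followed as written, the plan assures no scheduled, solicited adverse-event inquiry between the day 32 dose and Visit 4, a gap of nominally 14 days with a range of 4 to 24. That range rests only on the plan's own dosing days and visit window. The expected consequence is some under-recording of brief, mild symptoms after the repeat course in both arms, with a bias toward no difference on the primary endpoint. This assumes that such symptoms are less completely reported the later they are asked about. The amount lost cannot be derived from the documents, and no power figure should be attached to it. The sections also disagree on when the calls occur, so primary-endpoint data could be collected differently depending on which text staff follow. This is a cheap improvement, not a flaw that undermines the trial.

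**What to change.** Reconcile the call timing in the synopsis (both places), Section 6.0, Section 10.8 and Appendix B, and fill in the blank window cell. State a purpose and a day range for each of the three existing calls:

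1. An adverse-event call shortly after day 2.
2. A reminder call before the second course, which can also ask about adverse events.
3. An adverse-event call within a few days after day 32.

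Add one open item to the electronic form already in use, for example: any new or worse symptom since the last form? Say who reviews positive answers and how they are entered on the adverse-event form.

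The cost is small. No calls or visits are added. One reminder call becomes an adverse-event call, and positive form answers need follow-up by staff.

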6.1 Blinding

Blinding will be maintained through study follow-up until the last subject has been seen at 18- months and data has been analyzed. All study subjects and Study Team members responsible for subject evaluation, data management and analysis (including the Principal Investigator) will be blinded. In addition, any individual engaged by the Principal Investigator to provide radiographic, laboratory testing and and/or verification of data will be blinded to treatment.

Those unblinded include the Group Allocation Manager (not a member of the Study Team) that will be responsible for maintaining group assignment. In addition, the pharmacist responsible for medication distribution (including their team) will maintain a similar log and need to be unblinded to distribute study medication accurately.

6.2 Non-Prohibition of Additional/Alternative Procedures

In the event that a subject feels that he/she is unresponsive to the Study Medication (Fisetin or placebo) and/or and is having difficulty managing knee pain, he/she will be free to receive a single corticosteroid intra-articular knee injection and still remain in the study. In addition, subjects will be free to seek alternative treatment at any time; however, this may necessitate withdraw from the study as further described in **Section 14.3** of this protocol.

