7.5.2 Study Duration

When every treated subject has reached 18 months following treatment, the study will be considered complete, and the data will be summarized. It is estimated that enrollment will take approximately 18 months. Each study subject will be followed for 12 months, which will be considered the final visit. The PROs will be administered electronically at 18 months. The total duration of Study is approximately 36 months. An additional 4 months will be spent closing the study database and in data analysis.

The proposed start date is December 1, 2019, with anticipated last visit September 1, 2022.

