8.2.2 Secondary Endpoints

Statistically significant as compared to placebo:

1. Improvement in serum measures of inflammation and cartilage degenerating SASP markers;
2. Improvement in lower-extremity kinematic testing with video-motion analysis; isokinetic dynamometry testing, functional performance testing, ROM;
3. Improvement in IKDC, Lysholm, TEGNER, WOMAC and SF-12 surveys;
4. Improvement in the quality of articular cartilage in the knee joint as measured by T2 and T1rho relaxometry;
5. Days from day one of Study Medication intake to conversion to alternative therapy.

Additionally, we will review and discuss any possible correlation among secondary endpoint results.

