10.6 Additional Remote Follow-up

In addition to the in-clinic follow-up visits above, the following remote follow-up will be conducted:

10.6.1 Once Every 3 days During FIRST 6 weeks of Study Medication then Once a Week for an ADDITIONAL 6 weeks

Subjects will complete an augmented NRS questionnaire.

10.6.2 18-Months After First Dose of Study Medication (+/- 4 weeks)

Subjects will complete the augmented PROs electronically, including: NRS, IKDC, Lysholm, TEGNER, WOMAC and SF-12 questionnaires.

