15.0 Statistical Considerations

15.1 Study Overview, Aims and Objectives

The aim of this study is to perform a single-center randomized clinical trial (RCT) to test whether the dietary supplement Fisetin (FIS) can improve symptoms, kinematic function and soft tissue quality in patients with knee osteoarthritis. The proposed therapeutic systemic mechanism of FIS in this population is by selectively killing senescent cells that have been shown to associate with aging and age-related disease, including osteoarthritis (OA).

Assessments occur over 18 months following enrollment, and include safety monitoring, biomarker assessment, kinematic testing, quantitative MRI, knee-related patient reported outcomes, and observation of conversion to alternative treatment modalities. We hypothesize that the FIS treated group will not experience adverse events at a higher rate than the placebo group. Additionally, we hypothesize that improved OA disease status will be observed among the several pain, function and tissue quality endpoints for the FIS group when compared to the placebo group.

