15.5.2.4 Conversion to Secondary Interventions

In important endpoint for subjects enrolled in this study will be conversion to alternative treatments. The protocol allows for a single intra-articular corticosteroid injection into the knee to manage knee pain without necessitating removal of the subject from the study. However, if a study subjects elects to convert to a regenerative medicine treatment (e.g. platelet rich plasma or bone marrow aspirate concentrate) or a surgical intervention (e.g. microfracture or total joint replacement), they will be removed from the study. Cox proportional hazards regression will be performed to compare the hazard rate of conversion to each of these two treatment categories between treatment groups.

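### Conversion to alternative treatment is listed among assessments over 18 months, but no scheduled contact after month 12 is shown to ask about it, and no censoring time is stated

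*Combined protocol and SAP*

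**What the plan says.** - **Permission.** Under section 6.2, a subject who sees no response or cannot control the knee pain is covered by this rule: "he/she will be free to receive a single corticosteroid intra-articular knee injection and still remain in the study".
- **Endpoint.** Section 8.2.2 defines secondary endpoint 5 as "Days from day one of Study Medication intake to conversion to alternative therapy".
- **Period.** Section 15.1 states "Assessments occur over 18 months following enrollment" and includes in its list "observation of conversion to alternative treatment modalities".
- **Analysis.** Section 15.5.2.4 distinguishes the single permitted steroid injection from regenerative or surgical treatment, and plans: "Cox proportional hazards regression will be performed to compare the hazard rate of conversion to each of these two treatment categories between treatment groups". Neither 15.5.2.4 nor 15.7 states a censoring time.
- **Consequence of converting.** Regenerative or surgical treatment leads to removal from the study. The steroid injection is allowed "without necessitating removal of the subject from the study".
- **Contacts.** Section 7.5.2 says: "Each study subject will be followed for 12 months, which will be considered the final visit". For month 18, section 10.6.2 says: "Subjects will complete the augmented PROs electronically, including: NRS, IKDC, Lysholm, TEGNER, WOMAC and SF-12 questionnaires".
- **Schedule table (Appendix B).** Concomitant medications are recorded at Visits 1, 2, 4, 5, 6 and unscheduled visits. Adverse events are reviewed at Visit 3, the phone calls, Visits 4, 5, 6 and unscheduled visits. Both rows are blank in the 18-month column.
- **Form.** The one questionnaire reproduced (Appendix C) asks about pain, limp, stiffness, motion and function. It has no question on treatment received.

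**The concern.** A time-to-event endpoint needs someone to ask about the event for as long as subjects are counted at risk. Through month 12 this is in place: Visits 4, 5 and 6 review medications, history and adverse events. After that, the only scheduled contact is an electronic questionnaire set, and nothing in the documents shows that it asks about treatment.

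The steroid injection is the easiest conversion to miss, because it does not remove the subject and so leaves no administrative trace. Regenerative or surgical treatment leads to removal only once the site learns of it. Section 9.0 also admits community volunteers, whose later care may be elsewhere.

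Three things are at stake: the number of events behind a secondary comparison that is already small, the ability to tell a lasting effect from a postponement, and a clear rule for when an unheard-from subject stops being at risk. The primary endpoint is not affected.

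**Working it through.** **The plan's own figure.** The only sample-size calculation is for T1rho. With SMD 0.73, two-sided alpha 0.05 and 80% power, the normal approximation gives 2 × (1.960 + 0.842)² / 0.73² = 29.5, so 30 per group, as stated. Section 15.6 adds 6 per group for dropout, giving 36. The plan gives no figure for conversion.

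**Share of time.** Months 12-18 are 6 of 18 months, or one third.

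**Assumptions for an illustration (only 36 and 20% come from the plan).** 36 per arm; 20% lost, evenly over 18 months; 28% of placebo and 14% of fisetin subjects converting by month 18; constant hazards; all conversions pooled into one event.

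1. Monthly hazards: placebo −ln(0.72)/18 = 0.01825; fisetin −ln(0.86)/18 = 0.00838. Hazard ratio 0.46.
2. Converted by month 12: placebo 1 − 0.72^(2/3) = 19.7%; fisetin 1 − 0.86^(2/3) = 9.6%.
3. Share of conversions falling in months 12-18, before dropout: (42.0 − 29.2)/42.0 = 30%.
4. Expected events with capture to month 18. For a subject lost at a uniform time, the chance of an observed event is 1 − p18/(18 × hazard), which is 14.8% on placebo and 7.2% on fisetin. Placebo: 36 × (0.8 × 0.280 + 0.2 × 0.148) = 9.1. Fisetin: 36 × (0.8 × 0.140 + 0.2 × 0.072) = 4.5. Total 13.7.
5. Expected events with capture to month 12 only, by the same method: 6.6 + 3.2 = 9.8.
6. Rough standard error of the log hazard ratio, √(1/events on placebo + 1/events on fisetin): √(1/9.13 + 1/4.55) = 0.57 with full capture; √(1/6.63 + 1/3.22) = 0.68 to month 12.

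The formula in step 6 is slightly optimistic with so few events. Simulated Cox fits (3,000 trials per setting) gave:

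| Capture | Events | Median SE(log HR) |
|---|---|---|
| To month 18 | 13.6 | 0.59 |
| To month 12 only | 9.8 | 0.71 |
| 18-month item answered by 80%, the rest censored at Visit 6 | 12.8 | 0.61 |

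The median hazard ratio was 0.45 with full capture and 0.46 to month 12, so there is no material bias under proportional hazards.

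**Sensitivity to the assumptions.**
- At 15%/8% converting: 7.4 events with full capture, 5.2 to month 12, 6.9 with the item.
- Share of conversions in months 12-18: 11-17% if conversions come early, 28-32% at constant hazard, 39-44% if the hazard rises.
- At the plan's ceiling of 100 subjects (50 per arm), events scale by 50/36: about 19 and 14. The relative loss is the same.

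**Does an effect last?** Suppose fisetin only postpones conversion: hazard ratio 0.46 to month 12 and 1.5 after. The simulated median hazard ratio is 0.75 with full capture, 0.46 with capture to month 12, and about 0.7 with the item. Capture to month 12 cannot tell this case from a lasting effect.

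**The case against.** **The 18-month horizon is not firm.** The same sentence in 15.1 also lists biomarkers, kinematics and MRI, all of which end at month 12. Endpoint 5 and the Cox plan name no horizon, and 7.5.2 calls month 12 the final visit. Following conversion to Visit 6 only is a coherent reading. This stands. A reader might infer that the plan breaks a clear 18-month commitment, and the documents do not support that. They leave the horizon open, which is itself a reason to state it.

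**Capture at month 18 may exist in text not seen.** Section 6.0 ends with a cut-off sentence about collecting adverse-event and deviation data, which may refer to that contact. Under 12.1, a new escalation in treatment counts as an adverse event. The other 18-month forms are not reproduced. This stands as a caveat. Against it, Appendix B leaves the relevant 18-month cells blank.

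**Other routes.** Section 10.7 documents unscheduled contacts, and 18.1 provides two calls and a certified letter after a missed evaluation. Some subjects remain the investigators' own patients. These would catch some conversions, but none is a scheduled question about treatment to a subject who simply returns the questionnaire.

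**Little is lost.** At a hazard ratio of 0.46, standard errors of 0.59 and 0.71 correspond to power of roughly 26% and 19%, so the comparison is weak either way. Fitting each treatment category separately, as planned, leaves fewer events still. This also stands, and it limits the point to a modest improvement.

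**Stronger readings that do not hold.** A reader might infer that conversion proportions will be understated. That needs silent subjects to be counted as event-free to month 18, a rule the plan never states; Cox regression ordinarily censors at last observation. A reader might also infer that pain scores after an injection undermine the 12-week pain model. Under the intent-to-treat statement in 15.4 they are analysed as observed, which is valid; unequal injection rates would at most modestly dilute a difference. An extra model excluding those scores would answer a no-injection question that the protocol does not pose, on a missing-at-random assumption that cannot be tested.

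**Conclusion.** The point holds in a limited form. Section 15.1 places observation of conversion within an 18-month programme, but the last scheduled review that would reveal a conversion is at month 12, and no censoring time is given. Later conversions would be known mainly if volunteered or treated at the clinic.

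The consequence is lost precision, not bias. Under the assumed 28%/14%, about 10 events are captured instead of 14, and the standard error rises from about 0.59 to 0.71. The trial would also be unable to show whether an effect on conversion lasts beyond month 12. Conversion rates, timing and the postponement scenario are all assumptions, since the documents give none. The conclusion also depends on the 18-month contact being as Appendix B shows it. This is worth considering as an inexpensive improvement to a secondary endpoint.

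**What to change.** 1. Add one item to the existing 18-month questionnaire: since your last study visit, have you had a knee injection, a regenerative treatment or knee surgery (type, date, which knee)?
2. In 15.5.2.4, state that conversion is followed to month 18, and that a subject who does not answer the item is censored at the last contact where conversion was assessed, normally Visit 6.

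The Cox model, the permission to inject, the removal rule and the visit schedule stay as they are.

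**Cost.** One question and one or two sentences, with IRB agreement under 18.7. The answer is self-reported. Because both windows are ± 4 weeks, recall covers about 4 to 8 months, so dates will be approximate. Responders and non-responders may differ, and censoring non-responders at Visit 6 does not remove that. If the sponsor prefers to follow conversion only to month 12, saying so in 15.1 and 15.5.2.4 settles the horizon at no cost, but gives up the later events.
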